8.0 Ethics and Dissemination

Research Ethics Approval

Research ethics approval has been granted by the West of Scotland Research Ethics Committee (REF: 17/WS/0221).

Protocol Amendments

The views from members of the PMG will be sought on any proposed amendments to the Actissist protocol. Following this any proposed amendments will be submitted to the Study Sponsor and Research Ethics Committees for approval. Protocol amendments will be added to the Actissist Protocol and to the ISRCTN Registry.

Consent

Only those who agree to provide written informed consent will be included in the study. All potential participants, including service users and staff, will be provided with a copy of a Participant Information Sheet and Consent Form that includes a contact number for the study team.

For individuals joining Actissist that have been referred from CARMS, signing Appendix 2 of the CARMS Consent form gives permission for CARMS to share their final assessment data with the Actissist research team. Additionally, Appendix 1 of the Actissist Consent form permits the Actissist team to request the final CARMS follow up assessment data. The reciprocal documents for Actissist participants choosing to join the CARMS study have also been developed. See Method, page 8.

A separate consent form will be provided for individuals who only wish to take part in the EMIS or qualitative interviews about technology use.

Confidentiality

The confidentiality of all study data will be ensured via the following security mechanisms.

- **Software systems, interface and compliance with UK security standards:** three general principles of information security (confidentiality, integrity and availability) will be followed in the design and implementation of Actissist. All data transmitted to and from Actissist servers will be encrypted over https with strong ciphers as detailed in the Approved Cryptographic Algorithms Good Practice Guidelines (NHS, 2012 and Australian Equivalence). Cipher suites will be implemented in compliance with Section 6 (“Preferred uses of cryptographic algorithms in security protocols”) of the Good Practice Guidelines. In cases where participant data are downloaded from the Actissist sites, these data will be securely encrypted with a pass phrase of appropriate length and complexity. Data transfers are secured by using standards web security protocols. Uploading data to a central server in real time enables study data to be captured and so protects against data loss such as a phone, which can be

lost or stolen. This removes the need for personal data storage on the device. The purpose of the server in this case is secure data storage.

- **Software systems, interface and security compliance standards:** a range of measures is in place to help ensure the security of the Actissist and ClinTouch apps and the data generated by its users. The apps are hosted on a University of Manchester web server and has standard measures in place to prevent unauthorised access. We will also incorporate ISO 25010 which provides for safety-in-use and measures satisfaction with security. These security measures correspond closely to the NHS standards with which Actissist and ClinTouch currently comply.
- **Additional security measures:** There are a number of technical measures we will employ to protect personally identifiable data. Any data stored on the phone by the participant will be encrypted. We will also recommend that service users set a passcode to access their Smartphone. All service users recruited to the study will give their informed consent, and this will include risks to data security. These measures should be sufficient to prevent unauthorised data access, should the phone be lost or stolen.
- **Other study data:** any hard copy/ paper copy information will be stored in locked filing cabinets at local sites and will only be directly accessible by the PI and the study RAs and Project Officer. Directly identifying participant information (e.g., consent forms) and de-identified data will be stored in separate locked filing cabinets. Data will be entered onto a secure web-based portal hosted by University of Manchester.
- **Type of information stored:** the security arrangements and access for the code will be as follows. Each participant's dataset will have a unique code and will be stored in a password-protected database. The unique code will be linked to the participant's name and contact details. The information linking the participant's unique code and contact details will be stored separately from the study database and will also be password protected.

Dissemination Plan

We will produce an Actissist Dissemination Policy. This document will outline a comprehensive list of possible papers with basic descriptions of objectives, contents, authorship, and journals to be targeted.

Dissemination will occur via a number of methods, which include publication of trial papers, conference presentations and possible book chapters. Participants will be informed of the results by being offered written and/ or face-to-face feedback.

Appendix 1

PROTOCOL FOR MANAGING DISCLOSURE OF RISK **Randomised controlled trial participants** **Qualitative study participants**

Rationale

During a session or other contact with Actissist research staff a participant may indicate an intention to harm themselves or others. Participants may also provide information to the effect that a child or other vulnerable person may be in danger. Any information of this nature **must** be acted upon.

At the beginning of each research interview/assessment the participant will be informed that what is discussed is private and confidential except if they indicate any current intention to harm themselves or others, or if they provide information to the effect that a child or other vulnerable person may be in danger. In such situations the staff member has a legal duty to report this information.

Procedure

In the case that the participant indicates current intention to harm themselves or others, the researcher must remind the participant of their duty of care to break confidentiality (as already outlined at the commencement of the interview), unless there are circumstances that would contraindicate telling the participant of the need to break confidentiality (e.g. risk to safety of staff). The researcher must then pass this information on to a member of the participants clinical care team. The immediacy of this action will be dependent on individual circumstances.

If an imminent risk is identified, immediate action should be taken and the session should change focus to the imminent threat. However, if the participant reports that they intend to place themselves or others at risk of harm at some point in the distant future, action by the researcher may involve continuing with the session in light of the information discussed, reviewing how they are feeling at the end of the session and calling a member of the care-team following this. A similar course of action should be taken if a participant reports a historic risk event, which has not already been reported to their care team (e.g. a previous suicide attempt), this will include following flowchart 3.

If the participant indicates that a child / other vulnerable person may be in danger, in addition to contacting the participants care team, the respective Child or Adult Safeguarding Team should also be contacted (see contact details below). In either case the participant should be informed that confidentiality needs to be broken and, if at all possible, will be encouraged to work in collaboration with the relevant staff member to this end.

If the identification of risk (on-going or unreported historic) occurs during a face to face contact the individual may be given the option of phoning the care co-ordinator themselves in the presence of the staff member or staying in the room whilst a call is made. Alternatively, the individual may choose to wait in a safe place such as an adjoining room (if this is possible). Based upon the telephone discussion, the researcher will follow any reasonable request made by a member of the care team.

If a risk is identified and the care co-ordinator, psychologist and / or psychiatrist are not contactable (and such a course of action is recommended by clinical members of the research team), a call should be made within the hours of 9am – 5pm Monday to Friday to the duty worker for the appropriate Community Mental Health Team. Outside of the duty

workers working hours a call should be made to the Crisis Team or if necessary accompanying the participant to A&E. Contact details are listed in Appendix 2. Once again, the researcher will act in accordance with any action plan agreed and any reasonable request made by the clinical care team. This may involve faxing information over to A&E, accompanying the individual to A&E, etc.

If risk is disclosed during telephone contact, the individual will be informed that confidentiality will need to be breached. The same plan as above will be implemented and the individual should be called back to feedback the planned actions.

In the event that the individual discloses that a child / vulnerable adult may be in danger, the Child / Adult Safeguarding Team should be contacted. In all cases where a child or vulnerable adult is thought to be at risk researchers must adhere to the trusts safeguarding policy. If it is outside of 9am – 5pm and there is considered to be imminent risk to a child / vulnerable adult the police should be informed. However, the appropriate safeguarding team should also be informed. Details of out of hours Child / vulnerable Adult Safeguarding Team services are listed in Appendix 2.

If the researcher is uncertain as to the appropriate course of action to take they should initially contact the project lead ([name]). If the project lead is unavailable, flow diagram 3 should be followed. In the unlikely event that all avenues are exhausted the worker should follow the previously outlined plan (commencing with contacting the Care Co-ordinator).

If the participant or someone else has committed a crime then it may be necessary to phone the police as soon as possible. If the client is currently harming him or herself or has done so recently, and there is a need for medical attention, it would be important to negotiate with the client that they attend hospital or that they allow an ambulance to be called. If the client refuses to seek medical attention and there is a serious (e.g. life-threatening) and immediate risk to the participant's health an ambulance should be called. If the injury is not deemed to pose a serious and immediate risk to health, the participants care team should be contacted. The mental health team or duty psychiatrist would ensure that anyone refusing medical attention was assessed under the Mental Health Act. A decision regarding the need for a compulsory admission to hospital will then be made by an approved social worker in accordance with the Mental Health Act 1983.

Ensure that you record all information and actions taken, including telephone calls and discussions with your project lead/clinical supervisor, in the participant's file.

FACTORS TO CONSIDER IF A PARTICIPANT EXPRESSES HARM TO SELF OR OTHERS

If a participant you are working with expresses ideas of harm to self or others these are important factors to consider and pass on:

[figure not shown]
- Ideation (frequency, intensity, duration, triggers)
- Plans/intent
- Access to means to carry out plans
- Timeframe
- Protective factors

- Access to support/isolation
- Hopelessness
- Drug or alcohol use
- Command hallucinations and perceived power or control over voices

Any concerns you have should be discussed with the project lead as soon as possible. If your project lead is unavailable contact another clinical member of the research team ([name], [name], or [name]).

[figure not shown]
**FLOWCHART 1: CONTACTS FOR PARTICIPANTS
WITH IDENTIFIED INTENT TO HARM OTHERS**

**In situations where a Child / vulnerable Adult is at risk the appropriate
Safeguarding Team should be contacted.**

*Contacting emergency services (e.g. police) is the last resort and this option should only be exercised if all other options have been tried (or this course of action has been advised by clinically trained researchers) and there is a clear indication of an imminent risk to others.

**FLOWCHART 2: CONTACTS FOR PARTICIPANTS
WITH IDENTIFIED IMMINENT SUICIDAL INTENT**

[figure not shown]

**Accompany the participant to A & E if they are willing to attend. Insurance purposes do not permit the transporting of patients in researcher's vehicles. Consequently in this circumstance it may be necessary to call a taxi, walk, or phone an ambulance.*

****Contacting emergency services (e.g. police) is the last resort and this option should only be exercised if all other options have been tried (or if this course of action has been advised by clinically trained researchers) and there is a clear indication of an imminent risk to self.**

FLOWCHART 3: CONTACTS FOR PARTICIPANTS

WHO EXPRESS SUICIDAL IDEATION OR UNREPORTED HISTORIC RISK INFORMATION

**Accompany the participant to A & E if they are willing to attend. Insurance purposes do not permit the transporting of patients in researcher's vehicles. Consequently in this circumstance it may be necessary to call a taxi, walk, or phone an ambulance.*

****Contacting emergency services (e.g. police) is the last resort and this option should only be exercised if all other options have been tried (or if this course of action has been advised by clinically trained researchers) and there is a clear indication of an imminent risk to self.**

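### When a participant discloses, outside 9am–5pm, an intent that puts a child or vulnerable adult at imminent risk, the Appendix 1 text and the Flowchart 1 footnote give unreconciled rules on contacting the police

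*Protocol*

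**What the plan says.** All the relevant text is in the protocol's Appendix 1 on managing disclosure of risk.

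- **Procedure, child or vulnerable adult in danger.** The safeguarding team should be contacted. Outside 9am–5pm, if "there is considered to be imminent risk to a child / vulnerable adult the police should be informed". The safeguarding team is then to be told as well. Researchers must also follow the trust's safeguarding policy in every such case.
- **Procedure, self-harm needing medical attention.** The first step is negotiation: "it would be important to negotiate with the client that they attend hospital or that they allow an ambulance to be called". If the person refuses and "there is a serious (e.g. life-threatening) and immediate risk to the participant's health an ambulance should be called".
- **Procedure, crime.** Where a crime has been committed, "it may be necessary to phone the police as soon as possible".
- **Footnote to Flowchart 1 (intent to harm others).** "Contacting emergency services (e.g. police) is the last resort and this option should only be exercised if all other options have been tried". The sentence goes on to allow a second route, advice from clinically trained members of the research team. By either route it also requires a clear indication of imminent risk to others. A separate note on the chart directs the researcher to the safeguarding team where a child or vulnerable adult is at risk.
- **Footnotes to Flowcharts 2 and 3 (suicidal intent; suicidal ideation or unreported historic risk).** These carry the same last-resort rule and the same advice route, with the condition that "there is a clear indication of an imminent risk to self". A neighbouring footnote lists an ambulance, beside a taxi or walking, as a way of taking a willing participant to A&E.

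**The concern.** The text and the footnote treat imminence differently. In the text, once it is outside 9am–5pm and a child or vulnerable adult is involved, a judgement that the risk is imminent is enough for the police to be informed. In the Flowchart 1 footnote imminence is necessary but not sufficient: either the alternatives must have been tried, or a clinically trained colleague must have advised the call.

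The safety of a third party is at stake. Research assistants use this procedure under pressure and probably consult the chart and the text separately. Two trained people could follow the same appendix faithfully and act differently on the same disclosure.

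**Working it through.** No arithmetic applies. The check sets the rules side by side, case by case.

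**Main case: the participant intends harm, a child or vulnerable adult is at imminent risk, and it is outside 9am–5pm.**

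1. *Does the text apply?* Yes. Its conditions are the hour, the type of person at risk and imminence. It does not ask who poses the danger, so a participant's own intent is included.
2. *Does Flowchart 1 apply?* Yes. It is titled for participants with an identified intent to harm others, and its own note mentions children and vulnerable adults.
3. *What does the text direct?* The police should be informed, with no prior contact required.
4. *What does the footnote direct?* Police contact needs imminence and one of two things: the alternatives tried, or clinical advice obtained.
5. *Where do they diverge?* When imminence is established but neither of those two has yet happened. The text then directs the call and the footnote withholds it. Once either has happened, the two agree.
6. *Does anything settle the matter?* No. The Procedure says imminent risk calls for immediate action but does not say what the action is. A researcher who is unsure is to contact the project lead and, if the lead is unavailable, to follow the third flow diagram. That chart is titled for suicidal ideation or unreported historic risk, and its footnote repeats the last-resort rule for risk to self. Neither route says which rule prevails.

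**Neighbouring cases.**

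- *Same disclosure within 9am–5pm.* The safeguarding paragraph names only the safeguarding team, so it gives no police instruction to conflict with the footnote.
- *A child in danger from someone other than the participant.* The text applies. Flowchart 1, by its title, does not. No conflict is shown.
- *Serious injury with care refused.* The text says an ambulance should be called. This meets the Flowchart 2 and 3 footnotes only if two things hold: suicidal intent, ideation or unreported historic risk is also present, and emergency services there include an ambulance. The footnotes give police as their example and do not settle the second point.
- *Willing participant going to A&E by ambulance.* The charts allow it without the last-resort condition. No conflict.
- *Crime committed.* The text is permissive, so it sets no requirement that a footnote could contradict.

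**The case against.** The strongest reply is that a specific child-protection rule standing beside a general default is naturally read as an exception to it. Flowchart 1 has its own note for children and vulnerable adults, and the text sends researchers to the trust's safeguarding policy, which is not reproduced and may settle the point. The flowchart boxes are not visible in the text available, so a separate branch for imminent or out-of-hours risk cannot be ruled out. The project lead and named clinical colleagues are there to be consulted.

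Much of this is fair, and it limits the point. It does not remove it. The protocol does not say that the safeguarding sentence is an exception. Flowchart 1's note names only the safeguarding team and is silent on the police. Taking clinical advice is a step before the call that the text does not require. The two statements that disagree are both legible, whatever the boxes contain.

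The reply succeeds against broader readings. A reader might infer that the text demands a direct call in every named emergency while the charts forbid it until everything else has failed. The documents do not support that. The footnotes offer clinical advice as an alternative route, the crime sentence is permissive, and the ambulance instruction follows negotiation and refusal.

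**Conclusion.** The conflict is real but narrow. It is established for one situation: a participant whose disclosed intent puts a child or vulnerable adult at imminent risk, outside 9am–5pm. It operates until the alternatives have been tried or clinical advice has been given. The ambulance question is a secondary ambiguity that depends on how emergency services is read.

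The conclusion rests on two assumptions: that risk judged imminent in the text and a clear indication of imminent risk in the footnote describe the same state, and that the unseen boxes do not resolve the overlap.

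A reader might infer that every out-of-hours disclosure about a child or vulnerable adult is affected, or use the share of the week outside working hours as a measure of size. Neither follows. Flowchart 1 is limited to the participant's own intent, and clock hours say nothing about how often such disclosures occur. Delay is a plausible consequence that the protocol neither states nor allows to be measured. Nothing here touches the primary outcome, the analysis or the sample size. The wording should still be corrected, because it belongs to an operative safety procedure.

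**What to change.** The sponsor's clinical leads should reconcile the out-of-hours police sentence and the ambulance sentence in the Appendix 1 Procedure with the footnotes to Flowcharts 1, 2 and 3. The amended text should:

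- state which rule prevails where they overlap;
- say whether emergency services in the footnotes includes an ambulance;
- use the same wording in the Procedure and in each footnote.

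Which rule stands is a clinical and safeguarding decision, and this review takes no position on it. The cost is a small wording amendment to Appendix 1, its approval under the protocol's amendment process, and a re-briefing of the research assistants. There is no consequence for data or sample size.

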APPENDIX 1: DISCLOSURE OF RISK DURING AN INTERVIEW

PROCEDURE: DISCLOSURE OF RISK DURING AN INTERVIEW

Researchers are to follow these guidelines in the event that, when conducting an interview, they identify that a participant might be at risk, or could pose a risk either to themselves or to others. The examples presented herein are not prescriptive and should be modified according to the situation.

- **Prior to commencing an interview** with a participant, the researcher will carefully explain that, although the interview is going to be confidential, if any risk is identified or disclosed during the interview, then the researcher will have to communicate these concerns to other professionals:

"Before we begin the interview, I just want to explain again that what we will talk about will be confidential. However, if I feel that from what you say there might be a risk to either yourself or other people I will need to pass this on to other staff members. But if I do this, I will tell you".

- If during the interview a participant's account indicates that they might be distressed or they disclose some type of suicidality or risk factors for suicidality, the researcher will reflect the distress they appear to be in and will ask if they want to continue the interview, and/or offer a brief break:

"You seem to be going through a hard time at the moment – do you want to continue with the interview? You know we can take a break at any time or we can stop if you want to".

"It sounds like there have been a few things upsetting you recently – are you okay to continue with the interview or would you prefer to take a bit of a break for a few minutes?"

- If during the interview the participant has disclosed a clear risk of suicidality (for instance, a description of plans for self-harming, or explaining that they are in possession of medication to take an overdose), at the end of the interview the researcher will explain the need to communicate this to staff:

"You've spoken about wanting to take an overdose with some medication you have, and it sounds like you are quite upset about some of the things we've been talking about. What I'm going to do, like we'd talked about at the beginning, is to speak

with your care co-ordinator and tell them how you are feeling so that they know what's going on for you and so that they can help you"

- If during the interview the participant's account indicates or suggests a possible risk of suicidality (for example, talking about occasional fleeting feelings of wanting to die, or sometimes wishing they could just be gone to end their problems), the research assistant will try to ascertain some further information:

"You've said that you sometimes wish you could just be gone and end your problems, have you recently had this kind of thought? Do you mean that you have a plan for this or are they just thoughts?"

"You said that you sometimes have felt like you want to die – if you were to feel like this again, do you think you would communicate this to staff?"

At the end of the interview, the research assistant will talk about this with the participant:

"You said that sometimes you have felt like you want to die, although not in the last week – do you mind if I just mention this to your care co-ordinator, so that they are aware too?"

If the participant accepts, this information can be given to staff.

If the participant declines, the researcher will contact [name] in the first instance (and then [name], [name], or [name] if [name] is unavailable), to consult with them, on a case-by-case basis, the need to report this to staff.

- If any risk of suicidality has been disclosed by a participant during an interview and this risk needs to be reported to the care team, the researcher will do so verbally to a member of the care team:

"During a research interview, [participant's name and surname] has described plans and intent to take an overdose if access to medication was available. This was communicated to [staff name and role]. [Participant] is aware that I have passed this information on to their care team."

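### The interview risk procedure sets one end-of-interview timing for clear suicide risk, with no imminence check or pointer to the main procedure's immediate-action rule

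*Protocol*

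**What the plan says.** Two texts in the protocol's Appendix 1 deal with risk disclosed during research contact.

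**Main risk procedure** (protocol for managing disclosure of risk, which follows section 8.0). Its title names both randomised-trial and qualitative participants, and its rationale speaks of every interview or assessment: "At the beginning of each research interview/assessment the participant will be informed" of the limits of confidentiality. Under Procedure it says that how quickly the care team is told depends on the individual case, and then sets the rule for the urgent case: "If an imminent risk is identified, immediate action should be taken and the session should change focus to the imminent threat". It describes carrying on with the session for participants who "intend to place themselves or others at risk of harm at some point in the distant future". It adds: "A similar course of action should be taken if a participant reports a historic risk event" that the care team does not yet know about. Flowchart 2 is titled for identified imminent suicidal intent.

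**Interview procedure** (Appendix 1: Disclosure of risk during an interview). Researchers are told to follow it when they identify possible risk in an interview. Its opening paragraph adds that the examples are not binding and should be adapted to the situation. If the participant seems distressed or discloses suicidality, the researcher "will ask if they want to continue the interview, and/or offer a brief break". For a clear risk, with examples such as plans for self-harm or "explaining that they are in possession of medication to take an overdose", the instruction is that "at the end of the interview the researcher will explain the need to communicate this to staff".

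**The concern.** A researcher who hears a clear disclosure in an interview has two texts to hand. The one written for interviews gives a single time for the researcher's step and does not separate a participant at risk now from one who is not. The main procedure makes that separation and requires action at once on the imminent side of it.

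The examples of clear risk in the interview procedure are ones that could be imminent: a plan, or the means already in hand. A researcher working from the interview text alone would find no prompt to ask about timing and no reference to the rule that overrides the end-of-interview step. What is at stake is the safety of a participant in that situation. Nothing in the trial's design, data or estimates depends on it.

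**Working it through.** No formula applies to the main point, so the texts are set side by side.

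| Situation | Main procedure | Interview procedure, clear-risk step | Consistent? |
|---|---|---|---|
| Intent placed in the distant future | Session may continue, review at its end, then call the care team | Explain at the end of the interview | Yes |
| Unreported past event | Similar to the above | Explain at the end, if treated as clear risk | Yes |
| Imminent risk | Act at once and turn the session to the threat | Explain at the end of the interview | No |

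1. *Do both texts govern the same contact?* Yes. The main procedure covers qualitative participants and each interview or assessment. The interview procedure covers interviews and is to be followed.

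2. *Can the clear-risk step reach imminent cases?* Yes. The protocol's list of factors to consider includes plans or intent, access to means, and timeframe. The examples in the step supply the first two. Timeframe, which would separate imminent from non-imminent risk, is not asked about.

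3. *Is imminence checked elsewhere in the interview procedure?* No. The offer of a break ("will ask if they want to continue the interview, and/or offer a brief break") asks about the participant's willingness, not about danger. The follow-up questions on recency and planning are attached to a possible risk, the lower tier. The clear tier has none.

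4. *Is there a pointer?* No. The interview procedure refers neither to the immediate-action rule nor to Flowchart 2. By contrast, the main procedure links risk disclosed by telephone explicitly: "The same plan as above will be implemented and the individual should be called back to feedback the planned actions". The clear-risk step appears complete in the text, so the missing pointer does not look like a loss in PDF reading.

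5. *How many interviews are in reach?* Section 3.0 (Qualitative measures) plans more than 20 exit interviews. Section 2.0 (Sample size calculation) expects at least 5 interviews with people who decline or withdraw early.
   - No overlap: more than 20 + 5 = more than 25.
   - Full overlap: more than 20. Overlap is possible because the exit-interview sample is itself meant to include people who dropped out or refused.
   - Trial assessments are not counted, because the interview procedure speaks only of an interview.

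   These are counts of interviews, not of events. The protocol gives no expected number of disclosures that are both clear and imminent, and that number may be zero.

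**The case against.** The strongest reply is that the two texts can be read together. The main procedure holds the specific rule for imminent risk and applies to these interviews. A general step on clear risk, which is not the same as imminent risk, would normally be read subject to it. The interview procedure also says its examples should be adapted to the situation. And the step times the explanation to the participant. Reporting to the care team has its own step, with no delay written into it.

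Much of this stands. A researcher who applies the main procedure acts correctly, and for non-imminent risk the texts agree. What remains is that the adaptability sentence speaks of examples, whereas the end-of-interview timing is in the instruction itself, and that sentence supplies neither a test of imminence nor a reference to the rule. The sample script has the researcher announce at that same moment that the care co-ordinator will be told, so the report would naturally follow the delayed explanation.

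A reader might infer more than the documents support:

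- *That the protocol tells researchers to carry on with an interview despite imminent danger.* It does not say so, and the main procedure says the opposite.
- *That holding medication is in itself imminent risk.* The protocol does not define it that way; access to means is one factor among several.
- *That the opening script, which promises to tell the participant of any disclosure to staff, is a further contradiction, because the main procedure allows for cases where telling is contraindicated.* The script is sample wording and matches the main procedure's default of telling the participant. Changing it would be a drafting preference.

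The flowcharts' content is not shown, so how far they close the gap in practice cannot be judged.

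**Conclusion.** The point holds in a limited form. The clear-risk step gives a single, later timing for disclosures that can include imminent risk, and neither tests for imminence nor refers to the rule requiring immediate action. The inconsistency is confined to imminent cases, and the adaptability sentence and the scope of the main procedure soften it without removing it.

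This is a participant-safety wording correction that should be made. It rests on two readings: that clear risk, as exemplified, can include imminent risk, and that both texts apply to the same interviews. The number of participants affected is unknown and may be none. The case for acting is that the possible harm is severe while the correction is very small. Sample size, power, error rate and the interpretation of results are untouched.

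**What to change.** Amend the clear-risk step in Appendix 1: Disclosure of risk during an interview, so that it reads:

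*The researcher will ask about intent, timeframe and access to means. If the risk is or may be imminent, the session changes focus at once and the main procedure (including contacting the project lead if uncertain) and Flowchart 2 are followed. Otherwise,* "at the end of the interview the researcher will explain the need to communicate this to staff".

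This uses the main procedure's own response to imminent risk, a change of focus, and keeps its existing route for a researcher who is unsure. It leaves the present timing in place for non-imminent risk. The reference to Flowchart 2 relies on that chart's title alone, so the study team should confirm that its content fits.

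The cost is a small text edit and a short re-briefing of interviewers. The opening script can stay as it is. Design, data collection and analysis do not change.
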